9.2. Planned Virology Statistical Analyses

qVC data will be summarized for subjects who are culture positive at baseline. For the RT-PCR summaries for Flu A and Flu B combined, coinfected subjects values will be averaged.

The following is a list of viruses detected in the multiplex assay:

- Adenovirus
- Coronavirus 229E
- Coronavirus HKU1
- Coronavirus OC43
- Coronavirus NL63
- Human Metapneumovirus
- Human Rhinovirus/Enterovirus
- Influenza A
- Influenza A/H1
- Influenza A/H1-2009
- Influenza A/H3
- Influenza B
- Parainfluenza 1

- Parainfluenza 2
- Parainfluenza 3
- Parainfluenza 4
- RSV A+B

For the viruses with multiple subtypes, the data will be summarized by same virus family (e.g. corona virus, parainfluenza, and RSV, influenza A)

The list of mutations which includes but is not limited to H275Y will be provided only if the data is available.

11. APPENDICES

Section	Appendix
RAP Section 4	Analysis Populations
Section 11.1	Appendix 1: Protocol Deviation Management and Definitions for Per Protocol Population
RAP Section 5	: General Considerations for Data Analyses & Data Handling Conventions
Section 11.2	Appendix 2: Time and Events
Section 11.3	Appendix 3: Assessment Windows
Section 11.4	Appendix 4: Treatment States & Phases
Section 11.5	Appendix 5: Data Display Standards & Handling Conventions
	Study Treatment & Sub-group Display Descriptors
	 Baseline Definitions & Derivations
	Reporting Process & Standards
Section 11.6	Appendix 6: Derived and Transformed Data
	General, Study Population & Safety
	• Efficacy
	Pharmacokinetic
	Pharmacodynamic and or Biomarkers
Section 11.7	Appendix 7: Premature Withdrawals & Handling of Missing Data
	Premature Withdrawals
	Handling of Missing Data
Section 11.8	Appendix 8: Values of Potential Clinical Importance
Section 11.9	Appendix 9: Examination of Covariates and Subgroups
Section 11.10	Appendix 10: Multiple Comparisons and Multiplicity
Section 11.11	Appendix 11: Model Checking and Diagnostics for Statistical Analyses
Other RAP App	endices
Section 11.12	Appendix 12: Abbreviations & Trade Marks
Section 11.13	Appendix 13: List of Data Displays
Section 11.14	Appendix 14: Example Mock Shells for Data Displays

11.1. Appendix 1: Protocol Deviation Management and Definitions for Per Protocol Population

No Per Protocol Population will be used in the analysis.

11.2. Appendix 2: Time & Events

11.2.1. Protocol Defined Time & Events

Table 15 Time and Events Table: Assessments at Baseline and During Treatment

	Eligibilit y Assess ments		During Treatment - 5 days ^a Inpatient								
Procedures		Baselin e/ Study Day 1ª	Study Day 2	Study Day 3	Study Day 4	Study Day 5 /day of last dose ^a	Study Day 6 if applicab le ^b				
Written informed consent	Х	X									
Subject demography	Х	X									
Physical examination ^c		X	Х	Х	Х	Х	Х	Daily			
Influenza Test – locally performed (equipment provided by GSK)	Х	X									
Medical/Prior Medication/Drug/Smoking History	Х	X									
HIV and Liver Disease History ^d	Х	Х									
Influenza symptomse	X	X									
HIV, Hep B and Hep C Test ^f	Х										
Chronic underlying illness assessment	X	Х									
Inclusion/Exclusion Criteria	Х										
Safety/Efficacy Assessments											
Chest X-ray ^g		X									
ECG ^h	Х	X				Х	Х				
Adverse events		X	X	X	X	Х	Х	Daily			
Concomitant medications ⁱ		X	Х	Х	X	X	Х	Daily			
Complications of influenza/associated antibiotic use ^j		X	Х	X	Х	X	Х	Daily			
Vital signs (temperature, HR, BP, respiratory rate, oxygen saturation, ventilation status) ^k	Х	Х	Х	Х	X	Х	Х	3 x Daily			

	Eligibilit y Assess ments		During Treatment - 5 days ^a Inpatient								
Procedures		Baselin e/ Study Day 1ª	Study Day 2	Study Day 3	Study Day 4	Study Day 5 /day of last dose ^a	Study Day 6 if applicab le ^b				
Flu PRO		X	X	X	X	X	Х	Daily			
Katz Activities of Daily Living		Х	Х	Х	Х	Х	Х	Daily			
Activity level ^m		Х	Х	Х	Х	Х	Х	Daily			
Chemistry including Liver Function Tests (Local+Central) ⁿ	X	Х		Х		X	Х	Day 6,7,8			
Serum creatinine (Local+Central) °	Х	Х	Х	Х	Х	Χ	Х	Day 6,7,8			
Hematology (Local+Central) p	Х	Х		Х		Х	Х	Day 6,7,8			
Urine Output q		Х	Х	Х	χ	Х	Х				
Pregnancy testr	Х	Х						PT Day 3			
Nasopharyngeal swabs		X		Х		X	X	Day 8,12,16, 20,24,28 ,32			
Nasal Swab ^t	Х	X									
BAL ^u		X		X		X X	X				
Endotracheal aspirate ^v		Х		X		X	X	Day 8,16,24, 32, 45			
Nasal SAM strips (biomarkers) ^w		X		Х		X	X	Day 8,16,24, 32, dischar ge or Day 45			
Nasal washes ^x		Х		Х		Х	Х	Day 8,16,24, 32, dischar ge or Day 45			
Exploratory Biomarkers (Blood Sample)		X		Х		X	Х	Day 8,16,24, 32, dischar ge or Day 45			
PK sample (Dried Blood Spot) ^y		Х		Х		X	X				
Genetics Sample (Blood Sample) ^z		Х									
Transcriptomics (Blood Sample) ^z		X		Х		X	Х	Day 8, 16, 24,			

	Eligibilit y Assess ments		During Treatment - 5 days ^a Inpatient							
Procedures		Baselin e/ Study Day 1 ^a	Study Day 2	Study Day 3	Study Day 4	Study Day 5 /day of last dose ^a	Study Day 6 if applicab Ie ^b			
								32, dischar ge or Day 45		
Study Treatments										
Administration of investigational medication (IV) and oseltamivir (oral) twice daily		X	X	X	X	X	X			

- a. A 'Day' is defined as a 24 hour period (Treatment Day), therefore depending on the start time of the first dose of IV DNX, a Treatment Day may span two calendar days.
- Day 6 assessments only applicable if last day of dose of randomized treatment is on Day 6 (i.e for subjects who
 received first dose after 12 noon on Baseline/Day 1.
- c. Physical exam to be performed twice daily for subjects in the sentine cohort.
- d. Enrollment into the study will be based on history of diagnosis of HIV and liver disease. Blood samples will be analyzed after enrollment to retrospectively determine if subject is HIV, Hep B or Hep C postivie; however, results will not be available until after completion of dosing.
- e. Influenza symptoms to be assessed only at baseline for inclusion.
- f. Enrollment into the study will be based on any history of diagnosis of HIV and liver disease.
- g. Chest X-ray at Baseline and whenever clinically indicated.
- h. ECG: For the ECG on Baseline/Day 1, one 12-lead ECG (can be done within approximately 24 hours prior to dosing). At Baseline and on Day 5 or last treatment day, a monitoring strip can be utilized if a 12-lead ECG cannot be performed.
- i. Concomitant medications for influenza treatment of the current episode to be recorded from Day -7 (i.e. one week prior to baseline), if available.
- Complications of influenza such as bacterial pneumonia, pneumothorax, pleural effusion, ARDS, myositis, encephalitis, myocarditis, and associated antibiotic use will be recorded on all assessment days.
- k. Vital signs and ventilation status to be assessed three times daily during the treatment period between approximately 8 AM and 8 PM.
- I. Katz ADL score collected once daily while hospitalized.
- M. Activity level to be recorded as one of three responses (bed rest, limited ambulation or unrestricted) everyday while hospitalized
- n. Chemistry panel including Liver Function Tests to be required once every other day during treatment (local testing (L) of LFTs for subject management as well as central laboratory testing (C)).
- Serum creatinine level required at Baseline and twice daily during treatment for subjects in the sentinel cohort. For all other subjects, serum creatinine level required at Baseline and once daily during treatment (local testing (L) for subject management as well as central testing(C)).
- Hematology panel including CBC with differential required every other day during treatment (local testing (L) for subject management as well as central testing(C))
- q. Urine output to be measured twice daily for subjects in the sentinel cohort.
- r. Ultrasensitive urine or blood pregnancy test required in women of childbearing potential prior to dosing and 3 days post last dose of study treatment.
- s. Nasopharyngeal swab will be used for influenza Subtype RT-PCR, qRT-PCR, quantitative culture and may also be used for rapid influenza diagnosis; Will also be used for viral genotyping and phenotyping if needed and multiplex PCR assay.
- t. Nasal swab collected for influenza diagnostic test or other local test for influenza diagnosis

- BAL samples (for biomarkers) are requested only if the procedure/sampling is being carried out for routine
 management of the patient and at any timepoint throughout the study
- Endotracheal aspirates (biomarkers/neutrophil counts) are required for subjects who are intubated.
- w. Nasal samples for biomarkers will be collected at the days indicated from all subjects using nasal SAM strips.
- x. An optional procedure, nasal wash, will be used to collect nasal samples from as many non-intubated subjects as feasible.
- y. PK samples will be drawn on Day 1 (pre-dose), Days 3 and 5 to coincide with PD measurements (nasal washes if done, endotracheal samples and a blood draw for exploratory biomarkers). In sentinel cohort 1 (less severe subjects with normal renal function), PK samples will be additionally drawn on Day 3 at pre-dose, and 0.5, 1 (end of infusion), 1.5, 2, 3, 4, 8 and 12 hours post-dose. **Note: PK draws must be collected from the opposite arm from the infusion arm.**
- z. Informed consent for optional substudies (e.g., genetic research and transcriptomics), must be obtained before collecting samples. In subjects who consent, a blood sample for genetic research is collected at the baseline visit, or at the earliest point possible during the treatment period for genetic research testing; blood samples for transcriptomics are taken on each of the indicated days and used to evaluate changes in transcriptome profiles.

Table 16 Time and Events Table: Post-Treatment and Post-Discharge Assessments

	Post-Discharge Visits/TCs and Assessments Outpatient a					
Procedures	PT Day 3 (Visit)	Study Day 8 (TC)	Study Day 15 (TC)	Study Day 22 (TC)	Study Day 30 (TC)	Study Day 45 (Visit)
Safety/Efficacy Assessments						
Adverse events	Х	Χ	Х	Х	Х	Х
Concomitant medications	Х	Χ	Х	Х	Х	Х
Brief Physical Exam	Х					X
Complications of influenza / associated antibiotic use ^b	Х	X	Х	Х	Х	X
Temperature	Х	Х	Х	Х	Х	Х
Other Vital signs (HR, BP, respiratory rate, oxygen saturation, ventilation status) ^c	Х					Х
Flu PROd	Daily through Day 14	Daily through Day 14	Х	Х	Х	Х
Katz Activities of Daily Livinge	Х	X	Х	X X	Х	X
Activity level ^f	Daily through Day 14	Daily through Day 14	X	Х	Х	Х
Laboratory Assessments						
Clinical chemistryincluding LFTs ⁹ (Local+Central)	X					X
Serum Creatinineh (Local+Central)	Х					Х
Hematology ⁱ (Local+Central)	Х					Х
Pregnancy testi	Х					
Nasopharyngeal swabs	Х					
Exploratory Biomarkers (Blood Sample) ^k	Х					Х
Transcriptomics (blood	Х					X

sample) ^I						
Nasal SAM strips	Х					Х
(biomarkers) ^m						
Nasal washes ^m	Х					Χ
Hospital Readmission Status	Х	Χ	Х	Х	Х	X

- a. Following discharge from hospital, outpatient clinic visit/TC schedule of assessments will be followed for those patients who are discharged before Day 45. For 5 days treatment, PT Day 3 will be the same as Day 8 and will be a clinic visit.
- b. Complications of influenza such as bacterial pneumonia, pneumothorax, pleural effusion, ARDS, myositis, encephalitis, myocarditis, and associated antibiotic use will be recorded on all assessment days.
- c. Vital signs and ventilation status will be assessed at clinic visits (PT Day 3 and Day 45).
- d. FLU PRO to be measured once daily through Study Day 14.
- e. Activities of Daily Living (Katz Scale) to be done at clinic visits and at TCs.
- f. Activity level assessed by reporting on a 3 point scale of bed rest (1), limited ambulation (2) or unrestricted (3) to be done daily through Study Day 14.
- g. Clinical chemistry including LFTs to be required once every other day until PT Day 3 (for LFTs, local testing for subject management until PT Day 3; central testing for all assessments, including at Day 45).
- h. Serum creatinine required once every day until PT Day 3 (local testing for subject management until PT Day 3; central testing for all assessments, including at Day 45).
- i. Hematology panel including CBC with differential required once every other day until PT Day 3 (local testing for subject management until PT Day 3; central testing for all assessments, including at Day 45).
- j. Ultrasensitive urine pregnancy test required in women of childbearing potential on PT Day 3.
- k. Blood samples will be collected for exploratory biomarkers at PT Day 3, and at Study Day 45.
- I. Blood samples for transcriptomics will be collected on PT Day 3 and Study Day 45 and are optional. Samples will be collected only from those subjects who provide informed consent for genetic research.
- m. Nasal samples for biomarkers will be collected at PT Day 3 and Study Day 45 from all subjects using nasal SAM strips. In addition, an optional procedure, nasal wash, will be used to collect nasal samples from as many non-intubated subjects as feasible.

11.3. Appendix 3: Assessment Windows

This study will not use assessment windows.

11.4. Appendix 4: Treatment States and Phases

11.4.1. Treatment Phases

Assessments and events will be classified according to the time of occurrence relative to study treatment, unless otherwise specified.

Treatment Phase	Definition
Pre-Treatment	Date< Study Treatment Start Date
On-Treatment	Study Treatment Start Date ≤ Date ≤ Study Treatment Stop Date
Post-Treatment	Date > Study Treatment Stop Date

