5.2. Exclusion Criteria

A subject will not be eligible for inclusion in this study if any of the following criteria apply:

CONCURRENT CONDITIONS/MEDICAL HISTORY (INCLUDES LIVER FUNCTION AND QTc INTERVAL)

1. Subjects who, in the opinion of the investigator, are not likely to survive the next 48 hours beyond Baseline;
2. Immunosuppression, whether due to primary immunosuppressive conditions, such as history of inherited immunodeficiency syndromes, HIV infection, or secondary conditions, such as immunosuppressive medication, stem cell or solid organ transplantation, or malignancy;
3. Documented current liver disease (including Hepatitis A, B, or C), or known hepatic or biliary abnormalities (with the exception of Gilbert's syndrome or asymptomatic gallstones);
4. QTc Criteria: QTcB or QTcF >480 msec or >500 msec with bundle branch block;
5. For subjects enrolled in the sentinel cohorts: diabetes mellitus and chronic kidney disease;
6. Subjects who require dialysis, or are on renal replacement therapies;
7. Subjects who require extra corporeal membrane oxygenation (ECMO) at baseline (enrolled subjects who subsequently require ECMO may continue in the study)
8. Women who are pregnant as determined by a positive human chorionic gonadotrophin (hCG) ultrasensitive test prior to dosing or women who are

breastfeeding;

CONCOMITANT MEDICATIONS

9. Subjects who received other treatments for influenza including vitaglutam, umifenovir, and neuraminidase inhibitors (oseltamivir, zanamivir, peramivir) for more than 72 hours during current acute illness;
10. Subjects who received any immunoglobulins within 6 months of screening or planned administration of any of these products during the treatment period.
11. Subjects treated with cytotoxic or immunosuppressive drugs within six months of study enrolment. Topical, intra-articularly injected, or inhaled glucocorticoids, topical calcineurin inhibitors or imiquimod are allowed.

RELEVANT HABITS

12. Known history of drug abuse within 6 months of study start.

CONTRAINDICATIONS

13. History of sensitivity to any of the study medications, or components thereof or a history of drug or other allergy that, in the opinion of the investigator or Medical Monitor, contraindicates their participation.

DIAGNOSTIC ASSESSMENTS AND OTHER CRITERIA

14. Absolute neutrophil count <1.0 Gi/L

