9.4.2. Safety Analysis

All safety analyses will be based on the Safety Population defined in Section 9.3.1.

Exposure to study medication, measured by the number of days on study drug, will be summarized by treatment arm. The proportion of subjects reporting adverse events (AEs) will be tabulated for each treatment arm. The following summaries of AEs will be provided:

Incidence and severity of All AEs;

Incidence and severity of treatment related AEs;

Incidence and severity of AEs leading to withdrawal from study;

Incidence of serious AEs (SAEs).

Laboratory data, vital signs and ECG data (absolute values and change from Baseline) will be summarized by visit and treatment group. In addition, the maximum post-baseline toxicity grade will be tabulated by treatment.

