11.5.2. Baseline Definition & Derivations

11.5.2.1. Baseline Definitions

Parameter		nts Considered As eline	Baseline Used in Data	
	Screening	Day 1	Display	
Vital Signs (temperature, HR, BP, respiratory rate, oxygen status, ventilation status)	Х	Х	Day 1	
12 Lead ECG	Х	Х	Day 1	
Laboratory parameters	Х	X	Day 1	
Nasopharyngeal Swab		X	Day 1	
Nasal Swab	Х	X	Day 1	
Nasal SAM strips (biomarkers)		X	Day 1	
Nasal wash biomarker		X	Day 1	
BAL biomarkers		Х	Day 1	
Serum Biomarkers		X	Day 1	
Katz ADL		X	Day 1	
Flu PRO		X	Day 1	

For all endpoints (unless stated otherwise) the baseline value will be the latest pre-dose assessment. This is generally expected to be from the Day 1 visit, although such values may be missing or unscheduled assessments may be performed before treatment start.

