11.6. Appendix 6: Derived and Transformed Data

11.6.1. General

Multiple Measurements at One Time Point

- Mean of the measurements will be calculated and used in any derivation of summary statistics but if listed, all data will be presented.
- If there are two values within a visit the value closest to the planned/target day for that visit will be used. If values are the same distance from the target then the mean will be taken.
- Subjects having both High and Low values for Normal Ranges at any post-baseline visits for safety parameters will be counted in both the High and Low categories of "Any visit postbaseline" row of related summary tables. This will also be applicable to relevant Potential Clinical Importance summary tables.

Treatment Start Date

Treatment start date is defined as follows:

 Treatment start date is the date entered onto the IP exposure CRF for when study treatment started.

Study Day

- Calculated as the number of days from initial study treatment start date :
 - Ref Date = Missing → Study Day = Missing
 - Ref Date < Treatment Start Date → Study Day = Ref Date Treatment Start Date
 - Ref Data ≥ Treatment Start Date → Study Day = Ref Date (Treatment Start Date) + 1

Note that Treatment Start Date is considered to be on Study Day 1 and the day before this is Study Day -1; i.e., there is no Study Day 0.

Post-baseline

Post-baseline refers to the combined time periods of On-treatment and Post-treatment.

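### A pre-dose laboratory result dated on the day of first dose is both baseline and post-baseline in the SAP, so it can set a subject's maximum toxicity grade

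*SAP*

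**What the plan says.** Four SAP rules meet here.

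- **Baseline (11.5.2.1):** for all endpoints unless stated otherwise, "the baseline value will be the latest pre-dose assessment". The table shows Day 1 as the displayed baseline for every parameter.
- **Treatment phase (11.4.1):** pre-treatment is "Date< Study Treatment Start Date" and on-treatment is "Study Treatment Start Date ≤ Date ≤ Study Treatment Stop Date". The start date itself is on-treatment.
- **Treatment start (11.6.1):** "Treatment start date is the date entered onto the IP exposure CRF for when study treatment started". It carries no clock time, and the same section makes it Study Day 1.
- **Post-baseline (11.6.1):** "Post-baseline refers to the combined time periods of On-treatment and Post-treatment".

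SAP 8.2.2 puts on-treatment and post-treatment assessments into the laboratory summaries unless otherwise noted. Among these is Table 3.15, the summary of maximum treatment-emergent toxicities for all laboratory parameters. SAP 11.5.3 also admits unscheduled visits to the maximum-toxicity tables. Protocol 9.4.2 says that "the maximum post-baseline toxicity grade will be tabulated by treatment". Neither document defines treatment emergent, and SAP 11.3 uses no assessment windows.

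**The concern.** A table of maximum toxicity after baseline should describe what happened once drug was given. Under these rules a sample drawn before the first infusion, on the same calendar date, enters that maximum. A maximum-grade display is the most exposed kind, because one early value can fix a subject's entry whatever the later values show.

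Eligibility allows such values. For neutrophils, the count on which the main mechanism-based risk is judged, Protocol 5.2 excludes only "Absolute neutrophil count <1.0 Gi/L". A subject may therefore enter at 1.0 to 1.3 Gi/L, which is Grade 1 on the DAIDS table in Protocol Appendix 5. Protocol 5.1 also admits ALT up to 8 times the upper limit of normal when bilirubin is below 1.5 times that limit.

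At stake is the attribution of pre-existing abnormalities to the treatment period in every arm. That raises all the rates and can narrow a difference between arms.

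**Working it through.** The plan gives no figure on this point to reproduce. The check applies its rules to a record and then sizes the effect.

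**1. Rules applied to one hypothetical subject.** The grades and clock times are assumed. First infusion is at 14:00 on Day 1.

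| Record | Grade | Phase by date (SAP 11.4.1) | Phase by date and time |
|---|---|---|---|
| Evening before Day 1 | 3 | Pre | Pre |
| Day 1, 09:00, pre-dose (the baseline) | 3 | On | Pre |
| Day 3 | 1 | On | On |
| Day 5 | 0 | On | On |
| Post-treatment Day 3 | 0 | Post | Post |

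- Maximum post-baseline grade by date: 3, set by the baseline record.
- Maximum by date and time: 1.
- If only grades above baseline count: none, under either phase rule.
- A sample taken at 22:00 before a first dose at 01:00 the next day is pre-treatment even under the date rule, so it is not affected.

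**2. Size of the date rule alone.** Let b be the proportion abnormal at baseline, d the rate of new abnormality after dosing, and p the share of baseline abnormalities still present after dosing. Assume that every baseline is dated on the day of first dose, and that subjects whose baseline abnormality clears have new events at rate d.

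- Rate under the date rule: b + (1−b)d
- Rate under a date-and-time rule: b[p + (1−p)d] + (1−b)d
- Difference: b(1−p)(1−d)

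This is an upper bound, because baselines from an earlier date contribute nothing. With b = 20% and d = 5% (neither is in the documents):

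| p | Date rule | Date and time | Inflation |
|---|---|---|---|
| 0 | 0.20 + 0.80×0.05 = 24% | 0.20×0.05 + 0.80×0.05 = 5% | 19 points |
| 80% | 24% | 0.20×(0.80 + 0.20×0.05) + 0.04 = 20.2% | 3.8 points |
| 100% | 24% | 0.20 + 0.04 = 24% | 0 |

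**3. Effect on a difference between arms.** Take assumed new-event rates of 5% and 15%. By date the table shows 24% and 0.20 + 0.80×0.15 = 32%, a gap of 8 points. By date and time:

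- p = 0: 5% and 15%, a gap of 10, so the date rule costs 2 points.
- p = 80%: 20.2% and 0.20×(0.80 + 0.20×0.15) + 0.12 = 28.6%, a gap of 8.4, so it costs 0.4 points.
- p = 100%: a gap of 8, so it costs nothing.

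**The case against.** The best reply is that the SAP, read as a whole, intends to separate pre-dose from post-dose values. The sentence above the phase table says that "Assessments and events will be classified according to the time of occurrence relative to study treatment, unless otherwise specified". SAP 11.5.3 uses planned time relative to dosing in summaries, and SAP 11.5.2.2 computes change from baseline from a post-dose visit value. This shows the intent, but it does not repair the rules. The phase definitions under that sentence compare dates only. The planned-time convention does not assign phases. The post-dose wording protects change from baseline and nothing else.

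A second reply is that the words treatment emergent in the title of Table 3.15 imply worsening from baseline. If programmed so, the pre-dose grade would drop out. The SAP does not say it, however, and Protocol 9.4.2 asks for a maximum grade with no such condition. What stands is uncertainty about how the table would be built: the mock shells, the sponsor's reporting standards and the monitoring committee's charter are not available here. The point therefore concerns the literal text and does not predict the output.

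A third reply is that programmers would simply leave Day 1 out. No rule says so, and it would be wrong for the sentinel cohorts. Their creatinine is taken at baseline and twice daily during treatment, so Day 1 may hold values from both sides of the first infusion.

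The reply on importance stands. SAP 2.1 makes every analysis descriptive, in 10 subjects, with all data listed. Table 3.19 and Figure 3.2 show neutrophil counts by visit, which lets a reader see the true sequence.

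**Conclusion.** The rules contradict each other as written, and a pre-dose laboratory grade dated on the day of first dose can become a subject's maximum in Table 3.15. Under the assumptions above, the date rule adds between 0 and 19 points to a rate and takes between 0 and 2 points off a 10-point difference, depending on persistence. No decision in this terminated study turns on it.

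Several stronger readings are tempting, and the documents do not support them.

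- **Every baseline is affected.** Only those dated on the day of first dose are; earlier dates fall in pre-treatment.
- **High and low normal-range counts are distorted.** SAP 11.6.1 has a convention for such rows, but Appendix 13 lists no table that would use it.
- **The full change from 5% to 24% is due to the date rule.** That holds only if no baseline abnormality persists. A persisting abnormality still counts after the date rule is mended, and removing it takes a separate grade-above-baseline rule.
- **One subject shifts an arm by 25 or 50 points.** With arms of about 4, 4 and 2 (expected from 2:2:1, not stated), these are 1/4 and 1/2. They reflect the small arms and do not measure this rule's bias.
- **Severe neutropenia could be overstated.** The entry limit means a qualifying baseline count can be at most Grade 1.
- **Adverse event tables share the fault.** Protocol 7.4.1.1 collects adverse events from the start of study treatment and lets earlier occurrences go to medical history, so they are largely protected.

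**What to change.** In SAP 11.4.1 and 11.6.1, state that the record used as baseline and all earlier records are pre-treatment and excluded from post-baseline. Where sample times exist, classify by date and time relative to the start of the first infusion. Where they do not, apply the baseline-record rule.

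As a separate change, define treatment emergent for Table 3.15 as a grade after the first dose that is above the baseline grade.

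SAP 11.4.2, on adverse events and concomitant medications, needs no change.

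The cost is a few sentences of SAP text and one comparison in the derivation program, made before unblinding as the SAP synopsis already requires. Protocol 6.7 records the date and time of each dose. Protocol 7.4.6 names only a visit date for laboratory sample labels, so clock times may be missing for some samples, which is why the fallback rule is needed.
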